# 7.9.8 Patient Safety Monitoring

Toxicity will be assessed every 21 days (+/- 1 day) whilst on study medication (and weekly during cycle 1 of phase I). Toxicity will be measured according to CTCAE v 4.0 (Appendix 4).

#### 7.10 Evaluation Criteria

## 7.10.1 Efficacy

Objective tumour response and time to progression will be measured according to the ACTG criteria (Appendix 1).

## 7.10.2 Measurability of Tumour Lesions at Baseline

Accurate documentation of the size and number of cutaneous lesions may be difficult.

An estimate of the number of lesions is recommended (see Appendix 1 for algorithm). The location of three to five marker lesions with the inclusion of bi-dimensional measurements where possible, should be selected by the Principal Investigator or a delegated clinician, recorded on standard body diagrams showing their relationship to body landmarks.

Documentation of tumour-associated oedema is also important. Photographs are an essential part of the evaluation including photographs of uninvolved areas of skin and allow assessment of changes in lesion colour and nodularity. Rulers must be included in the photographs.

Anonymised photographs, labelled only with patient's RNO, tumour site (labelled A – E as per the Kaposi Evaluation Form), visit and date of photograph, should be uploaded and emailed to the SCART Trial Mailbox within 2 weeks of being taken.

### 7.10.3 Tumour Response Evaluation

All patients will have their BEST RESPONSE from the start of study treatment until the end of 6 cycles of treatment classified as outlined in Appendix 1.

### 7.10.4 Frequency of Tumour Re-evaluation

Tumours (cutaneous, oral and visceral) will be re-evaluated every 6 weeks (+/- 1 day) during treatment. After 6 cycles of treatment responding patients will be offered the option of continuing selumetinib in combination with HAART. Following discontinuation of protocol treatment and the 30 Day Post-Discontinuation visit, patients who have not progressed will continue to be re-evaluated every 12 weeks (+/- 7 days) for up to 12 months.

# 7.10.5 Date of Progression

This is defined as the first day when the ACTG criteria for PD are met.

# 7.10.6 Reporting of Tumour Response

All patients included in the study must be assessed for response to treatment, even if there is a major protocol treatment deviation or if they are ineligible, or not followed/re-evaluated. Each patient will be assigned one of the following categories: complete response, partial response, stable disease, progressive disease, early death from malignant disease, early death from toxicity, early death from other cause or unknown (not assessable, insufficient data).

Early death is defined as any death occurring before the first per protocol time point of tumour reevaluation. The responsible investigator will decide if the cause of death is malignant disease, toxicity or other cause.

Patients for whom response is not confirmed will be classified as "unknown", unless they meet the criteria for stable disease (or the criteria for partial response in case of an unconfirmed complete

response). Patients' response will also be classified as "unknown" if insufficient data were collected to allow evaluation per these criteria.

## 7.10.7 Duration of Tumour Response

Response duration will be measured from the time measurement criteria for CR/PR (whichever is first recorded) are first met until the first date that recurrent or progressive disease is objectively documented.

## 7.10.8 Progression Free Survival

Progression free survival will be measured from the time of start of treatment until the criteria for progression are met (see ACTG criteria, Appendix 1).

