# 2.1.2 Secondary Objectives

- To describe the pharmacokinetics of selumetinib in combination with HAART, including the effects of selumetinib on HAART metabolism.
- To assess the toxicity of selumetinib in combination with HAART.
- To describe the pharmacodynamic effects of selumetinib in combination with HAART.
- Progression free survival rate at 6 months from commencing treatment.

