#### 2.2.2 Phase I & II

- Toxicity assessed by CTCAE v 4.0 criteria (see Appendix 4).
- Number of selumetinib cycles completed and PFS data will be collected as supportive data out to
   12 months from the last patient completing study treatment.
- Objective response rates assessed using ACTG criteria (see Appendix 1).
- Progression free survival rate 6 months from the start of study treatment assessed using ACTG criteria.
- Human immunodeficiency virus (HIV) control by HIV-1 viral load pre-treatment and weeks 3, 6, 12 and 18, and CD4 counts pre-treatment and at weeks 9 and 18.
- Pharmacodynamic measures of selumetinib in combination with HAART assessed by:
  - Serum concentrations of angiogenesis markers including serum Ang-2, IL-6 and VEGF assessed by ELISA pre-study and on weeks 3, 6, 12 and 18.
  - Biopsies pre-study and at week 6 to assess pERK levels in tumour tissue and other downstream markers including c-myc, c-fos, changes in apoptosis markers such as Bad and Bcl-2, and adaptive changes in PI3K/Akt and other MAPK pathways such as JNK and p38.
- Analysis of peripheral blood mononuclear cells (PBMCs) collected in a sub-study at selected centres pre-treatment and at weeks 9 and 18.
  - Levels of pERK, down-stream targets c-fos and c-myc, and key apoptotic proteins Bad and Bcl-2 will be assessed by Western blotting of lysed viable PBMCs.
  - PBMCs will be challenged with TLR4 and 9 agonists and production of IL-1 $\beta$ , TNF- $\alpha$ , IL-6, IL-10, IL-12 and type 1 interferon will be measured by cytometric bead array of culture supernatants.
  - o ROS production by PBMCs will be measured by flow cytometry using dichlorofluorescein (DCF) and cell survival assessed by Annexin V-PE/TO-PRO3 staining and flow cytometry.

Page 18 of 61

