# **Progressive Disease (PD):**

The appearance of new lesions or new sites of disease.

An increase of 25% or more in the size of previously existing lesions.

A change in the character of 25% of more of the skin or oral lesions from macular to plaque-like or nodular.

The development of new or increasing tumour-associated oedema or effusion also represents disease progression.

(Adapted from Krown, Metroka et al. 1989).

SCART KAPOSI'	'S SAI	RCOMA EVALU			
This form is to be used to evaluate KS at baseline  At baseline identify 5 representative lesions (including oral and visceral lesions) to be reproducibly measured on follow up and indicate their location on the schematic below.  If present visceral disease should be included as at least one representative lesion.					
	Date	d d m m m	BASE y y	LINE ASSESSME	ENT
A	Lesion	Perpendicular Diameters (mm)	Product of Diameters (mm²)	Oed Present? Y/N	Grade? Mild – 1; Mod – 2; Severe - 3
// B // (\	Α	x			
Z C Z	В	x			
and   host	C	x			
	D	x			
	E	x			
		Sum of Products (mm²)		Grade total num	
	*Grad	e number of KS lesions: 0 - Noi 1- >0 : 2 - >1: 3 - >5	≤10 0 ≤50		

Date	d d m m m y y	Cycle#	Complete Response (CR):  The absence of any detectable residual disease, including tumour-associated oedema, persisting for at least 4 weeks.
Lesion	Perpendicular Product of Diameters Diameters (mm) (mm²)		Partial Response (PR):  A 50% or greater decrease in the number of previously existing lesions (skin, oral, measurable or
A	x	Evaluation of Nodularity:	evaluable visceral disease) lasting for at least 4 weeks without the appearance of new lesions or the appearance or worsening of tumour-associated oedema or effusions, or an increase of 25% or more in the product of bi-dimensional diameters of any indicator lesion.
В			A 50% decrease in the sum of the products of the perpendicular diameters of bi-dimensionally measurable marker lesions.
	X		Complete flattening of at least 50% of the lesions (i.e. 50% of previously nodular or plaque-like lesions become macules). In those patients with predominantly nodular lesions, flattening to an indurated plaque of 75% or more of the nodules will also be considered a PR.
С	x	Oedema Evaluation:	Whenever possible, responses should be documented with photographs.  Patients with residual tumour-associated oedema or effusion who otherwise meet the criteria for CR will be classified as having a PR.
D	x		Stable Disease (SD):  Any response not meeting the criteria for progression or PR.

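### PFS in section 7.10.8 ends only at ACTG progression, so it is time to progression under another name and the 6-month rate may be overstated

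*Protocol*

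**What the plan says.** Section 2.1.2 lists as a secondary objective "Progression free survival rate at 6 months from commencing treatment". Section 2.2.2 repeats it as an outcome measure: "Progression free survival rate 6 months from the start of study treatment assessed using ACTG criteria". Sections 13.2.1 and 13.2.2 say only that the 6-month figure will be reported.

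The definition is in section 7.10.8: "Progression free survival will be measured from the time of start of treatment until the criteria for progression are met", with a pointer to Appendix 1. On the date of progression, section 7.10.5 says: "This is defined as the first day when the ACTG criteria for PD are met". The progressive disease list in Appendix 1 covers new lesions or sites, growth of existing lesions, and change in lesion character. It closes with: "The development of new or increasing tumour-associated oedema or effusion also represents disease progression". Death is not on the list.

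Section 7.10.1 uses a different name for the measure: "Objective tumour response and time to progression will be measured according to the ACTG criteria".

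Deaths are provided for elsewhere. The response categories in section 7.10.6 include "progressive disease, early death from malignant disease, early death from toxicity, early death from other cause or unknown". Section 7.11 follows patients until death or for 12 months after treatment, and the Death Form in section 10.1 records date and cause.

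**The concern.** Progression free survival names a state that a patient leaves by progressing or by dying. The written definition lets a patient leave it only by progressing. A patient who dies without meeting the ACTG criteria never has an event, whatever the cause of death. The analyst must then either count that patient as progression-free at 6 months or censor at death, and the protocol does not say which. Both choices move the rate in the same direction, upwards or not at all.

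At stake is one named secondary endpoint and the supportive PFS data that section 12 collects for planning later trials. A 6-month PFS rate that does not register deaths from toxicity is a weak input to the randomised phase II/III study that section 1.5.2 has in view.

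**Working it through.** **Step 1. Can death be read into the definition?** Four places were checked.

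- Section 7.10.8: the end point is that the progression criteria are met.
- Section 7.10.5 and Appendix 1: those criteria concern lesions, oedema and effusion only.
- Section 7.10.6: early death from malignant disease, from toxicity and from other cause are categories separate from progressive disease. Even an early death from KS is therefore not classed as progression there.
- Synopsis and sections 2.1.2, 2.2.2, 12, 13.2.1 and 13.2.2: none makes death a PFS event or gives a censoring rule.

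As written, the endpoint is time to progression.

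**Step 2. The plan's own figures.** The protocol states no 6-month PFS target, expected rate or death rate, so there is no PFS figure to reproduce. Its only sample-size figures are for response (section 13.1.2): 16 then 25 patients, stop at 1 or fewer responses, accept at 5 or more, rates 10% and 30%. The probability of accepting at true rate p is

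sum over x = 2 to 16 of P(X1 = x) × P(X2 ≥ max(0, 5 − x)), with X1 ~ Bin(16, p) and X2 ~ Bin(9, p).

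This gives 0.0951 at p = 0.10 and 0.9030 at p = 0.30, within the stated 0.10 and 0.90. A minimax search returns the same design. Nothing in it depends on PFS.

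**Step 3. Size of the effect on the 6-month rate.** Inputs: n = 25 (section 13.1.2); k progressions and d deaths without documented progression by 6 months, both assumed; no other censoring before 6 months.

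- Death counted as an event: (25 − k − d)/25.
- Written definition, deaths counted as progression-free: (25 − k)/25. The excess is d/25, which is 4.0 points for one death and 8.0 for two.
- Written definition, deaths censored (Kaplan-Meier): from (25 − d − k)/(25 − d), if all deaths precede the first progression, up to (25 − k)/25, if all follow the last.

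| k | d | Death an event | Counted progression-free | Censored | Excess if censored (points) |
|---|---|---|---|---|---|
| 10 | 0 | 15/25 = 60.0% | 60.0% | 60.0% | 0 |
| 10 | 1 | 14/25 = 56.0% | 60.0% | 14/24 = 58.3% to 60.0% | 2.3 to 4.0 |
| 10 | 2 | 13/25 = 52.0% | 60.0% | 13/23 = 56.5% to 60.0% | 4.5 to 8.0 |
| 10 | 3 | 12/25 = 48.0% | 60.0% | 12/22 = 54.5% to 60.0% | 6.5 to 12.0 |
| 8 | 1 | 16/25 = 64.0% | 68.0% | 16/24 = 66.7% to 68.0% | 2.7 to 4.0 |
| 12 | 1 | 12/25 = 48.0% | 52.0% | 12/24 = 50.0% to 52.0% | 2.0 to 4.0 |

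The direction does not depend on the assumed values: for any d ≥ 0, (25 − d − k)/(25 − d) is at least (25 − d − k)/25.

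**The case against.** The strongest reply is that section 7.10.8 only starts the clock and points to the criteria for progression, leaving event and censoring rules to a SAP, which was not available here. The endpoint's name also argues against counting a dead patient as a progression-free survivor. This would carry weight if the protocol were silent. It is not: it states where PFS ends. A SAP that counted deaths would contradict that sentence, and one that followed it would keep the gap.

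A second reply is that the effect is small beside sampling error. At an assumed 60% in 25 patients the 90% half-width is about 1.645 × √(0.6 × 0.4/25) = 0.161, or 16 points, and no test or decision rule rests on PFS. That is true and limits the importance of the point. But the shift is one of definition, always in the favourable direction, and costs almost nothing to remove.

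Third, some deaths from KS would already carry a progression date, because patients are examined every 3 weeks on treatment and section 7.10.5 does not tie progression to scheduled evaluations. This stands and narrows the exposure. Deaths from toxicity or other causes remain exposed.

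A reader might also infer more than the documents support:

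- *That such deaths would not count against the regimen at all.* Under section 7.10.6 an early death is neither a complete nor a partial response, so it counts as a non-response for the primary endpoint in section 13.2.2.
- *That the result could not be set beside the chemotherapy PFS medians in section 1.1.* How those studies counted deaths is not stated, and the protocol plans no such comparison.
- *That duration of response in section 7.10.7 has the same fault, since it runs* "until the first date that recurrent or progressive disease is objectively documented". Its name does not promise survival, so ending it at recurrence or progression is not an error.

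**Conclusion.** The point holds as a mismatch between name and definition. Section 7.10.8 defines time to progression and calls it PFS, and no other section corrects it. The 6-month PFS rate may be overstated by up to 4 points for each death without documented progression within 6 months among 25 patients if such deaths are counted as progression-free, and by about 2 to 4 points for one death if they are censored, assuming 10 progressions.

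It would go too far to say that the rate is overstated. That requires at least one such death, and the protocol gives no death rate from which to predict one; with none, the two definitions give the same figure. The effect is confined to the secondary 6-month PFS rate and the supportive PFS data. The primary response endpoint, the sample size and the stopping rule are untouched.

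**What to change.** Reword section 7.10.8 so that PFS runs from start of treatment to the first of ACTG progression or death from any cause, with patients alive and progression-free censored at their last disease evaluation. Align section 7.10.1 by naming PFS there, or, if time to progression is also wanted, list it as a separate endpoint under its own name. Carry the same wording into the SAP. Section 7.10.7 needs no change.

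The cost is one or two sentences. No new visits, data or patients are needed, because section 7.11 already follows patients until death or for 12 months after treatment and the Death Form supplies date and cause. The downside is that the reported 6-month rate may be slightly lower.

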# 7.11 Patient Follow Up

- All patients will be followed-up on study until death or for 12 months after the end of treatment, whichever is sooner. Every 12 weeks (+/- 7 days) patients will have a physical examination and clinical photographs to assess disease response or progression.
- If visceral or extensive disease was identified at baseline, CT scans should be done every 12 weeks for 12 months post end of treatment, or until progression, whichever is sooner.

# 7.12 Patient Withdrawal

The Investigator will make every reasonable effort to keep each patient on study. However, if the Investigator removes a patient from the study treatment or if he or she declines further participation final assessments will be performed, if possible. These include a physical examination, laboratory samples, an assessment of AEs and disease response (if appropriate), recording concomitant medication and drug accountability. All the results of the evaluations and observations, together with a description of the reasons for study withdrawal, must be recorded in the CRF.

Patients who are removed from the study due to adverse experiences (clinical or laboratory) will be treated and followed according to accepted medical practice. All pertinent information concerning the outcome of such treatment must be recorded in the CRF.

The following are justifiable reasons for the Investigator to withdraw a patient from study:

- Unacceptable toxicity.
- Unforeseen events: any event which in the judgement of the Investigator makes further treatment inadvisable.
- SAE requiring discontinuation of treatment.
- Withdrawal of consent.
- Serious violation of the study protocol (including persistent patient attendance failure and persistent non-compliance).
- Withdrawal by the Investigator for clinical reasons not related to the study drug treatment.

Where patient is withdrawn early from trial treatment and is not evaluable, additional patients will be recruited to replace them.

# 8 TRANSLATIONAL RESEARCH

# 8.1 Objectives

 To relate clinical responses to selumetinib therapy in combination with HAART by evidence of substrate inhibition in tumour tissue by measurement of pERK.

• To investigate compensatory changes to accessory pathways including JNK, p38 MAPK and PI-3K/Akt pathways in tumour tissue.

- To demonstrate changes in expression of circulating pro-angiogenic factors in association with selumetinib therapy in combination with HAART.
- A sub-study using PBMCs will explore whether susceptibility to inhibition of ERK
  phosphorylation in KS tumour tissue can be predicted by measurement of pERK in peripheral
  blood mononuclear cells (PBMCs) and further identify changes in accessory MAPK pathways.
- To determine whether these changes modify constitutive or Toll-like receptor (TLR)-induced expression of pro-inflammatory cytokines, type 1 interferons and reactive oxygen species (ROS) in PBMCs and to repeat key findings in tumour specimens.
- To determine whether selumetinib in combination with HAART modifies PBMC susceptibility to apoptosis or levels of apoptotic cells in tumour samples.

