### **Blood Samples:**

- Angiogenic biomarkers on Cycle 1 Day 1 Pre-treatment, Cycle 1 Day 22/Cycle 2 Day 1, Cycle 2 Day 22/Cycle 3 Day 1, Cycle 4 Day 22/Cycle 5 Day 1 and Cycle 6 Day 22 (all +/- 1 day except Cycle 1 Day 1 Pre-treatment).
- HIV-1 viral load on Cycle 1 Day 1 Pre-treatment, Cycle 1 Day 22/Cycle 2 Day 1, Cycle 2 Day 22/Cycle 3 Day 1, Cycle 4 Day 22/Cycle 5 Day 1 and Cycle 6 Day 22, then at the end of every 3 cycles in patients continuing on selumetinib beyond 6 cycles (all +/- 1 day except Cycle 1 Day 1 Pre-treatment).
- CD4 count on Cycle 1 Day 1 Pre-treatment, Cycle 3 Day 22/Cycle 4 Day 1 and Cycle 6 Day 22, then at the end of every 3 cycles in patients continuing on selumetinib beyond 6 cycles (all +/- 1 day except Cycle 1 Day 1 Pre-treatment).
- PBMC sub-study on Cycle 1 Day 1 Pre-treatment Cycle 3 Day 22/Cycle 4 Day1 and Cycle 6
  Day 22 (participating centres only, all +/- 1 day except Cycle 1 Day 1 Pre-treatment).

Further details can be found in the Laboratory Manual.

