# Additional Assessments:

- Tumour biopsy End of Cycle 2 (+/- 1 day).
- Disease evaluation on Cycle 2 Day 22/Cycle 3 Day 1, Cycle 4 Day 22/Cycle 5 Day 1 and Cycle 6 Day 22 then at the end of every 2 cycles (all +/- 1 day) in patients continuing selumetinib using ACTG criteria (see Appendix 1), with clinical photographs.
- Echocardiogram or multi gated acquisition (MUGA) scan (measurement of LVEF) to be performed on Cycles 2 Day 22/Cycle 3 Day 1 and Cycle 4 Day 22/Cycle 5 Day 1 (both +/- 1 day). If a decrease of LVEF of >10% is observed, an additional assessment may be performed at the 30 Day Post-Discontinuation Visit (+/- 3 days) and every 6 weeks thereafter (+/- 7 days) whilst LVEF continues to remain >10% from baseline. Decreases in LVEF from baseline may be investigated according to the algorithm (Appendix 7).
- All new dyspnoea AEs or worsening of pre-existing dyspnoea AEs should be followed according to the dyspnoea algorithm (Appendix 8).
- Ophthalmologic exam to include slit lamp examination, measurement of visual acuity, assessment of visual fields, assessment of colour vision, and overall visual assessment – to be performed in patients experiencing visual disturbances whilst in the trial as clinically indicated (Appendix 9).
- CT imaging of assessable disease (where present) at the end of every 2 cycles (+/- 1 day).

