# 8.3.3 PBMC Sub-study

A sub-study will be undertaken in selected centres in 12 patients in total. In this sub-study requiring viable PBMCs, 50 mls of venous blood will be collected in Lithium Heparin tubes at Cycle 1 Day 1 Pretreatment, Cycle 3 Day 22/Cycle 4 Day 1 and Cycle 6 Day 22 (all +/- 1 day except Cycle 1 Day 1 Pretreatment) and couriered to Sheffield for analysis (please refer to the Laboratory Manual for courier details). Viable PBMCs obtained by FicoII-Paque density centrifugation will be cultured in 24 well plates. Samples will be split and aliquots will be lysed to obtain protein for Western blotting to measure levels of pERK in relation to ERK and of phosphorylation of key substrates in the JNK, p38 MAPK and PI-3K/Akt pathways. Changes to down-stream targets of ERK signalling, including c-fos and c-myc will be assessed along with key apoptotic proteins such as Bad and BcI-2. An aliquot of PBMCs will be challenged with TLR4 and 9 agonists or left untreated and production of IL-1 $\beta$ , tumour necrosis factor-(TNF)- $\alpha$ , IL-6, IL-10, IL-12 and type 1 interferons will be measured by cytometric bead array of culture supernatants. Reactive oxygen species (ROS) production by PBMCs will be measured by flow cytometry

using dichlorofluorescein (DCF) and cell survival assessed by Annexin V-PE/TO-PRO3 staining and flow cytometry.

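### The PBMC sub-study has no same-visit on-treatment blood–tumour pair: the biopsy is at week 6 and the blood draws are at weeks 9 and 18, so concurrent pERK inhibition cannot be compared.

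*Protocol*

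**What the plan says.** The aim is a bullet in Protocol section 8.1 that begins "A sub-study using PBMCs will explore whether susceptibility to inhibition of ERK". The same sentence then states what is to be predicted, and from what: "phosphorylation in KS tumour tissue can be predicted by measurement of pERK in peripheral" (meaning the PBMCs). It is worded as exploration, not as a formal test.

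The sampling times are stated consistently:

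- **Tumour.** Section 2.2.2 has "Biopsies pre-study and at week 6 to assess pERK levels in tumour tissue". The phase II list in section 7.9.2.2 has "Tumour biopsy End of Cycle 2 (+/- 1 day", and section 8.2 and the table in 7.9.7 agree. This is the only biopsy scheduled on treatment.
- **Blood.** Section 2.2.2 has "Analysis of peripheral blood mononuclear cells (PBMCs) collected in a sub-study at selected centres pre-treatment and at weeks 9 and 18". Section 7.9.2.2 has "PBMC sub-study on Cycle 1 Day 1 Pre-treatment Cycle 3 Day 22/Cycle 4 Day1 and Cycle 6", the last of these on Day 22. Section 8.3.3, after naming the pre-treatment draw, has "Cycle 3 Day 22/Cycle 4 Day 1 and Cycle 6 Day 22 (all +/- 1 day except Cycle 1 Day 1", so the window applies to the two later draws only. The table in 7.9.7 adds later draws for patients who continue beyond six cycles.
- **Size.** Section 8.3.3: "A sub-study will be undertaken in selected centres in 12 patients in total".

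No section schedules a PBMC draw at Cycle 2 Day 22/Cycle 3 Day 1, or a biopsy at week 9 or week 18.

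**The concern.** Asking whether pERK in blood can stand in for pERK inhibition in tumour calls most directly for both tissues to be read under the same drug exposure. On this schedule each on-treatment blood value comes at least one full cycle after the tumour value. Section 7.4 allows selumetinib to be held, reduced or stopped for toxicity, and any of these can fall between the two samples.

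If blood and tumour then disagree, the data cannot show whether the tissues respond differently or were read at different exposures or times. Each sub-study patient gives 50 ml of blood per draw and, where possible, an on-treatment biopsy. Taking the two apart gives up part of their value for a stated aim.

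**Working it through.** There is no stated sample size, power or error rate to reproduce for this aim. The check is one of timing.

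**Inputs**
- Cycle length: 21 days (section 7.2).
- On-treatment biopsy: end of Cycle 2, window ±1 day (7.9.2.2).
- On-treatment PBMC draws: end of Cycle 3 and end of Cycle 6, window ±1 day (7.9.2.2, 8.3.3).
- Sub-study size: 12 (8.3.3).

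**Nominal days from first dose.** The end of cycle k is 21 × k days.
- Biopsy: 21 × 2 = day 42 (week 6).
- First on-treatment PBMC draw: 21 × 3 = day 63 (week 9).
- Second on-treatment PBMC draw: 21 × 6 = day 126 (week 18).

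These agree with the weeks given in section 2.2.2.

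**Gap from biopsy to blood.** The minimum is (blood − 1) − (biopsy + 1). The maximum is (blood + 1) − (biopsy − 1).

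| PBMC draw | Nominal gap | Minimum | Maximum |
|---|---|---|---|
| Week 9 | 63 − 42 = 21 days | 62 − 43 = 19 | 64 − 41 = 23 |
| Week 18 | 126 − 42 = 84 days | 125 − 43 = 82 | 127 − 41 = 86 |

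The windows cannot bring the samples together, so by schedule 0 of 12 patients have a same-visit on-treatment pair. Both on-treatment draws come after the biopsy.

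**What the existing samples still allow**

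| Comparison | Available? | Limit |
|---|---|---|
| Day 1 blood pERK against week 6 tumour inhibition | Yes; blood comes first | Shows nothing about inhibition in blood. The pre-study tumour may be archived tissue (7.9.1), so it need not match Day 1 in time |
| Week 6 tumour against week 9 blood | Yes, in patients still being sampled at week 9 | Lag of 19 to 23 days; dosing may have changed |
| Inhibition in blood and tumour at the same time on drug | No | No common on-treatment visit |

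**With the week 9 draw moved to the biopsy visit.** Both samples fall on day 42 ± 1. The nominal gap is 0 and the largest is 43 − 41 = 2 days. The number of draws through Cycle 6 stays at three, and the volume stays at 3 × 50 = 150 ml.

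**The case against.** The strongest defence is that the schedule already serves the aim as written. The protocol speaks of susceptibility being predicted, and a Day 1 PBMC sample precedes the biopsy, so relating baseline blood pERK to week 6 tumour inhibition is a fair reading. A week 6 draw would be concurrent with the biopsy and would not supply an earlier predictor. This stands, and it limits the point to concurrent comparison.

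A reader might infer that no on-treatment pair exists at all, or that the aim cannot be addressed. The documents do not support that: a patient who stays on treatment has a week 6 tumour sample and a week 9 blood sample. A reader might also infer that pairs are lost selectively in non-responders, since the first disease evaluation listed in section 7.9.2.2 falls at the biopsy visit. That loss is possible, but stopping can equally follow toxicity, intercurrent illness or patient request (7.2, 7.12), and the protocol gives no rate for any of these. One patient is 1/12, about 8%, of the sub-study; that is not an estimate of loss.

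The week 9 draw also coincides with the CD4 count, and the same blood serves the TLR-challenge, cytokine, ROS and apoptosis assays. This is a real cost of moving it, but a small one, because no stated PBMC objective depends on week 9. Finally, a week 6 draw does not repair a baseline biopsy that may be archival. That is also true, and is a separate limit on the baseline comparison.

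**Conclusion.** The point holds in limited form. The single on-treatment biopsy and the nearest on-treatment PBMC draw are 21 days apart by design (19 to 23 with the windows). The degree of pERK inhibition in blood and tumour therefore cannot be compared at the same time on drug in any of the 12 patients. Baseline prediction and a lagged comparison remain possible.

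This rests on samples being taken as scheduled, with cycles of 21 days. It assumes nothing about how often doses change in the gap, which the protocol does not quantify.

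Severity is low. The aim is exploratory, is confined to selected centres, and is not named among the primary or secondary objectives in section 2.1. It has no bearing on the phase II response endpoint, the sample size or any decision rule. The reason to act is that the change is cheap.

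**What to change.** For patients not yet sampled, move the PBMC draw from Cycle 3 Day 22/Cycle 4 Day 1 to Cycle 2 Day 22/Cycle 3 Day 1. Keep the Day 1 pre-treatment and Cycle 6 Day 22 draws. Amend sections 2.2.2, 7.9.2.2, 7.9.7 and 8.3.3 and the Laboratory Manual to match. In the analysis, flag patients sampled on the old schedule and do not treat their week 9 blood as concurrent with the biopsy.

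**Cost.** The change is to schedule wording and the manual. It adds no visit, draw or volume, because the week 6 visit already includes blood for angiogenic markers and viral load. There are two downsides. The PBMC draw no longer coincides with the week 9 CD4 count. The 12-patient sub-study may also be split between two schedules: phase I is complete and the protocol does not say how many sub-study patients remain to be sampled, so the number who would benefit is unknown. If none remain, the limit should simply be stated when the blood–tumour comparison is reported.
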